The intervention consists of two parts, Options Counseling (OC) and Health Education (HE). The OC part includes family assessment, counseling and provision of emotional support, access assistance, and development of independent-living plans (care plans) using the Iowa's Heritage Area Agency on Aging database. The Options Counselor is trained to use motivational interviewing techniques to develop family care plans, provide emotional support, and connect families to available services and programs in the community. The HE part includes post-diagnosis family education using the 7-module health education toolkit developed specifically for this study based on the literature and expert reviews. OC-HE will conduct initial assessment to determine educational needs within 2 weeks of participant's randomization into the intervention group and develop initial care plan; and will conduct 5 monthly follow-up calls to adjust the care plan and provide educational components appropriate at each point. This intervention aims to create direct links between the medical clinics, home and community-based services (HCBS), and family.

Participants assigned to the usual care control group will participate in baseline, as well as 3- and 6-months

follow-up surveys. Those in usual care group will receive a general informational brochure from the Alzheimer's Association, and will be given an option of receiving a call from their local Options Counselor after completing the 6-month survey.

Study duration is about 18 months. We aim to start participant enrollment in August, 2019, complete recruitment by September, 2020, and complete data collection by March 2021. Each participant will be enrolled in this study for about 6 months from enrollment to final interview.

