10.0 Safety Reporting

Definition of Adverse Events

This protocol uses the definition of adverse event (AE) from the OHRP Guidance on Reviewing and Reporting Unanticipated Problems Involving Risks to Subjects or Others and Adverse Events: Any untoward or unfavorable medical occurrence in a human subject, including any abnormal sign (for example, abnormal physical exam or laboratory finding), symptom, or disease, temporally associated with the subject's participation in the research, whether or not considered related to the subject's participation in the research (modified from the definition of adverse events in the 1996 International Conference on Harmonization E-6 Guidelines for Good Clinical Practice). *See Adverse Event Form Appendix G*

Serious Adverse Events

This protocol uses the definition of serious adverse events (SAE) as defined in the OHRP Guidance on Reviewing and Reporting Unanticipated Problems Involving Risks to Subjects or Others and Adverse Events: Any adverse event that (1) results in death; (2) is life-threatening (places the subject at immediate risk of death from the event as it occurred); (3) results in inpatient hospitalization or prolongation of existing hospitalization; (4) results in a persistent or significant disability/incapacity; (5) results in a congenital anomaly/birth defects; or (6) based upon appropriate medical judgment, may jeopardize the subject's health and may require medical or surgical intervention to prevent one of the other outcomes listed in this definition. *See Serious Adverse Event Form Appendix H*

Responsibilities of NIA, IRB, DSMB, and Investigators

AEs will be reported to the University of Iowa IRB and NIA using an Adverse Event Form quarterly or as determined by the NIA. The members of the Data Safety Monitoring Board (DSMB) will receive this report prior to the scheduled board meetings.

Reporting Process

The occurrence of an adverse event (AE) or serious adverse event (SAE) may come to the attention of study personnel during interviews and intervention encounters. The PI will meet with the research team bi-weekly to conduct ongoing data and safety monitoring, and will meet bi-annually with the Data Safety Monitoring Board (DSMB) consisting of three external board members, Drs. [name], [name], and [name]. The PI will be informed of serious adverse events (SAEs) as soon as they occur and will notify the UI IRB and NIA within 24 hours of notification.

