All adverse events (AEs) will have their relationship to study procedures, including the intervention, assessed by an appropriately-trained clinician based on temporal relationship and his/her clinical judgment. The degree of certainty about causality will be graded using the categories below.

- **Related** – The AE is known to occur with the study procedures, there is a reasonable possibility that the study procedures caused the AE, or there is a temporal relationship between the study procedures and the event. Reasonable possibility means that there is evidence to suggest a causal relationship between the study procedures and the AE.
- **Potentially Related** – There is some evidence to suggest a causal relationship (e.g., the event occurred within a reasonable time after administration of study procedures). However, other factors may have contributed to the event (e.g., the participant's clinical condition, other concomitant events). Although an AE may rate only as "possibly related" soon after discovery, it can be flagged as requiring more information and later be upgraded to "probably related" or "definitely related", as appropriate.
- **Not Related** – There is not a reasonable possibility that the study procedures caused the event, there is no temporal relationship between the study procedures and event onset, or an alternate etiology has been established.

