APPENDIX G – ADVERSE EVENT FORM

Adverse Event Form

STUDY NAME

Site Number: _____

Pt ID: _____

Has the participant had any Adverse Events during this study? Yes No (If yes, please list all Adverse Events below)

Severity	Study Intervention Relationship	Action Taken Regarding Study Intervention	Outcome of AE	Expected	Serious
1 = Mild 2 = Moderate 3 = Severe	1 = Definitely related 2 = Possibly related 3 = Not related	1 = None 2 = Discontinued permanently 3 = Discontinued temporarily 4 = Reduced Dose 5 = Increased Dose 6 = Delayed Dose	1 = Resolved, No Sequel 2 = AE still present- no treatment 3 = AE still present-being treated 4 = Residual effects present-not treated 5 = Residual effects present- treated 6 = Death 7 = Unknown	1 = Yes 2 = No	1 = Yes 2 = No (If yes, complete SAE form)

Adverse Event	Start Date	Stop Date	Severity	Relationship to Study Treatment	Action Taken	Outcome of AE	Expected?	Serious Adverse Event?	Initials
1.									
2.									
3.									

Adverse Event

Form Version 1.0

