APPENDIX J – ADVERSE EVENTS/SERIOUS ADVERSE EVENTS LISTING

Data as of: _____

Date of report: _____

Participant ID	Onset Date	Stop Date	Expected (Y/N)	Relationship to Intervention* (Y/N)	Outcome**	Description of SAE

* *Definite, Possible, Not Related*

** *Outcome:*

Recovered, without treatment

Recovered, with treatment

Still Present, no treatment

Still Present, being treated

Residual effect(s) present – no treatment

Residual effect(s) present- being treated

Subject died

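### The adverse-event causality grades in Protocol section 10.0 overlap and contradict each other, with no precedence rule and differing scales on the forms

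*Protocol*

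**What the plan says.** Protocol section 10.0, under the terms used in reporting, says that the relationship of each adverse event (AE) to study procedures, with the intervention counted among them, is "assessed by an appropriately-trained clinician based on temporal relationship and his/her clinical judgment". Three grades follow.

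- *Related* has three alternatives joined by *or*: the event is known to occur with the procedures; there is a reasonable possibility that they caused it; "or there is a temporal relationship between the study procedures and the event". A reasonable possibility is then explained as the existence of evidence pointing to causation.
- *Potentially Related* requires some evidence pointing to causation. The example given is that "the event occurred within a reasonable time after administration of study procedures". Other factors may have contributed. The text adds that an event first rated possibly related may later be raised to probably or definitely related.
- *Not Related* is also a list of alternatives. Two of them are: "there is no temporal relationship between the study procedures and event onset, or an alternate etiology has been established".

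The same section defines an AE as an unfavorable occurrence "temporally associated with the subject's participation in the research", whether or not it is thought to be related. No time window is given for the causality grades, and no rule covers an event that meets more than one of them.

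The Appendix G form codes the relationship to the study intervention as "1 = Definitely related 2 = Possibly related 3 = Not related". The Appendix J listing has a column headed "Relationship to Intervention* (Y/N", and its asterisk leads to a footnote with the levels definite, possible and not related.

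On contacts, section 2.0 says "Participants assigned to the usual care control group will participate in baseline, as well as 3- and 6-months" surveys. Sections 2.0 and 7.0 add an initial session and five monthly calls for the intervention arm. The SAP's description of the intervention has an initial call and two monthly calls.

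**The concern.** A causality scale should give one grade per event, and two assessors who follow it faithfully should agree. Here they could assign opposite grades to the same event and both be right by the text. A code on Appendix G or J also does not tell the reader with certainty which section 10.0 grade was meant.

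AE reports go to the IRB and NIA, and to the DSMB before its meetings. Section 10.0 provides for DSMB data split by group. If timing alone can earn the top grade, the arm with more study contacts collects more such grades at equal true risk. This is a matter of grading. It is separate from the fact that the AE question is put at every intervention encounter, which affects how many events are found.

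**Working it through.** **1. Do the grades exclude one another?** Two test cases are enough.

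- An event soon after a session, with an established other cause. It meets *Related* (timing alternative) and *Not Related* (other-cause alternative). No precedence rule resolves this.
- An event within a reasonable time of a procedure, with possible contributing factors. It meets *Potentially Related*. It also meets *Related* twice: through timing, and through the reasonable-possibility alternative, which is explained in nearly the same terms as the evidence required for *Potentially Related*. Nothing in *Related* excludes contributing factors. Read literally, the middle grade has no events of its own, and deleting the timing alternative would not cure that.

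The lead sentence joins timing **and** judgment, while the definition of *Related* joins timing to its other alternatives by **or**.

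**2. Do the scales agree?**

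| Place | Levels | Referent |
|---|---|---|
| Section 10.0, grades | Related / Potentially / Not | study procedures, including the intervention |
| Section 10.0, text under *Potentially Related* | also possibly, probably, definitely | same |
| Appendix G | Definitely / Possibly / Not | study intervention |
| Appendix J | Y/N header; footnote Definite / Possible / Not | intervention |

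Controls do not receive the intervention during follow-up, so the referent on the two forms has no clear meaning for them.

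**3. How uneven could the timing alternative be?** The documents give no attribution figure, so there is nothing to reproduce. What follows is an illustration.

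Inputs from the documents:
- Control: 3 surveys (baseline, 3 and 6 months).
- Intervention, Protocol: 3 surveys + 1 initial session + 5 calls = 9.
- Intervention, SAP: 3 + 1 + 2 = 6.
- Recording runs to 7 days (AEs) or 30 days (SAEs) after last participation (section 10.0).

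Assumptions: surveys on days 0, 90 and 180; first session on day 14 (day 7 also tried), then every 30 days; recording period T = 180 + 7 = 187 or 180 + 30 = 210 days; window of w days after each procedure; coincidental events spread evenly over time, equally frequent and equally captured in both arms.

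Formula: share meeting the timing alternative = (days of T covered by the union of the windows) / T. The ratio is the intervention share divided by the control share.

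For T = 187 and first session on day 14:

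| w (days) | Control | Protocol arm | Ratio | SAP arm | Ratio |
|---|---|---|---|---|---|
| 7 | 21/187 = 11.2% | 63/187 = 33.7% | 3.0 | 42/187 = 22.5% | 2.0 |
| 14 | 35/187 = 18.7% | 119/187 = 63.6% | 3.4 | 77/187 = 41.2% | 2.2 |
| 30 | 67/187 = 35.8% | 187/187 = 100% | 2.8 | 127/187 = 67.9% | 1.9 |
| 60 | 127/187 = 67.9% | 100% | 1.5 | 157/187 = 84.0% | 1.2 |
| 90 | 100% | 100% | 1.0 | 100% | 1.0 |

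For T = 210, the ratios at 7, 14 and 30 days are 3.0, 3.0 and 2.3 (Protocol) and 2.0, 2.0 and 1.7 (SAP). Starting on day 7 changes the 14-day ratios to 2.7–3.0 and 1.8–2.0. Over windows of 7 to 30 days the range is therefore 2.3–3.4 (Protocol) and 1.7–2.2 (SAP).

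**The case against.** The strongest reply is that the rule is not mechanical. Section 10.0 requires a trained clinician's judgment as well as timing, and limits the assessment to people with the authority to diagnose. A sensible clinician would not call an event with a known other cause *Related*. This stands against the reading, tempting from the third alternative alone, that every event following a procedure will be graded *Related*. It does not rescue the definitions, because the lead sentence and the grade still disagree. Judgment is also not shown to be independent of arm: section 15.0 says the design involves no masking, section 9.0 blinds only the student interviewer/data entry assistant, and no blinding of the causality assessor is stated.

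A reader might also infer that over-attribution several times higher in the intervention arm is established. It is not. The ratio depends wholly on an assumed window, is about 2 on the SAP's schedule for short windows, and vanishes near 90 days. Nor can one argue both that the timing alternative separates nothing, because every AE is already temporally associated with participation, and that it separates the arms strongly. On the broad reading nearly all events in both arms qualify and the ratio is about 1; only a narrow window produces a difference.

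It would also be too strong to say that the forms cannot be mapped to section 10.0. The Appendix J footnote gives three ordered levels that match Appendix G, and three ordered levels can be lined up with three. The mapping is simply not stated, and the Y/N header conflicts with it.

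Finally, the consequences are limited. All AEs are documented whatever their relationship, SAEs go to the IRB and NIA within 24 hours without a relatedness filter, and neither document plans a between-arm comparison or a stopping rule based on the grade. The Protocol calls the trial minimal risk. All of this stands, and it limits how much the point matters.

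**Conclusion.** The point holds as an internal contradiction in a stated rule. One event can be both *Related* and *Not Related*, the two upper grades overlap, no precedence is given, and labels and referent differ between section 10.0 and Appendices G and J. This needs no assumption beyond reading the text.

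The direction of the arm imbalance follows if the timing alternative is applied literally with a window shorter than about 90 days, because the intervention arm has more procedures. Its size is illustrative only: about 2.3–3.4 on the Protocol's schedule and 1.7–2.2 on the SAP's for windows of 7 to 30 days, under even timing, equal event rates and equal capture. The documents do not support reading these as expected attribution rates.

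The effect is confined to safety attribution reporting. Efficacy analyses and SAE notification are untouched. The change should be made, because the text as written can misgrade events and the correction is cheap.

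**What to change.** In section 10.0:
- Make timing necessary but never sufficient for *Related*, in line with the lead sentence.
- Reword *Related* and *Potentially Related* so that they do not overlap, including the evidence-of-causation wording that they share.
- State that an established other cause takes precedence and gives *Not Related*.
- Remove the references to possibly, probably and definitely related, or adopt those terms as the grades.

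Use one three-level scale and one referent (study procedures, including the intervention) in section 10.0, Appendix G and Appendix J, and drop the Y/N header from Appendix J. With this change the timing clause by itself would produce no *Related* grade in either arm.

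The drafting cost is a few sentences and two relabelled forms. The real cost is regrading events already graded. Data collection was planned to end by March 2021 and the SAP is dated January 2022, so regrading may be post hoc. It is best done without knowledge of arm and reported as such.

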11.0 Study Compliance

This protocol defines a protocol deviation as any noncompliance with the clinical trial protocol, International Council on Harmonisation Good Clinical Practice (ICH GCP), or Manual of Procedures (MOP) requirements. The noncompliance may be either on the part of the participant, the investigator, or the study site staff. As a result of deviations, corrective actions will be developed by the site and implemented promptly.

These practices are consistent with ICH GCP:

- Section 4.5 Compliance with Protocol, subsections 4.5.1, 4.5.2, and 4.5.3
- Section 5.1 Quality Assurance and Quality Control, subsection 5.1.1
- Section 5.20 Noncompliance, subsections 5.20.1, and 5.20.2.

It will be the responsibility of the PI to use continuous vigilance to identify and report deviations within 14 working days of identification of the protocol deviation, or within 14 working days of the scheduled protocol-required activity. All deviations will be addressed in study source documents, and reported to the NIA Program Official. Protocol deviations will be sent to the reviewing Institutional Review Board (IRB) per their policies. The PI will be responsible for knowing and adhering to the reviewing IRB requirements. Only protocol deviations that impact participant safety will be reported within 24 hours of occurrence if possible, or as soon as they are discovered. All other deviations will be reported routinely to the DSMB and IRB. A form for documenting protocol deviations is included in Appendix K.

Protocol deviations/violations may include, but are not limited to, the following:

- Randomization of an ineligible participant
- Failure to obtain Informed Consent
- Failure to keep IRB approval up to date

A log for recording protocol deviations is included in Appendix K.

12.0 Data Collection and Study Forms

This section of the MOP describes the study's data collection and data management procedures. Copies

are included as appendices.

12.1 Participant Folder/Binder

While most of the study data will be monitored electronically, each participant will have a folder, stored in a locked file cabinet in Research Manager [name]'s office. The folder will include:

- Questionnaires completed by the participant (if applicable, most will be online) *Appendix L Baseline Interview*
- Case Report Forms (CRFs)/Reportable Event Form *Appendix M*
- Participant information form (if provided by the clinical team or for providing incentives) *Appendix N*
- Screening form *Appendix B*

The OC-HE will also keep a separate folder locked in a file cabinet in her office at the College of Public Health for each participant in the intervention group. This folder will include

- OC Assessment Tool *Appendix O*
- Care Plan *Appendix P*
- Completed HIPAA form *Appendix Q*
- Participant information form (if provided by the research team)

12.2 Study Forms

Form Name	When Given	When Collected	Appendix	Maintenance
Eligibility Screening	Read to potential participant by RA	Before potential participant receiving any materials	B	Kept in Participant Folder locked in [name]'s office
Study Flyer	In Research Packet after participant screens eligible	N/A	D	N/A
Study Summary	In Research Packet after participant screens eligible	N/A	E	N/A
Consent Letter	In Research Packet after participant screens eligible. Read through with Interviewer before baseline and revisited before 3 and 6 month follow up	N/A	F	N/A
Participant Contact Form	Given by clinicians when a potential participant appears to be eligible	At PWD appointment by clinicians, given to research manager	U	Kept in Participant Folder locked in [name]'s office

	(Research Manager will do eligibility screening)			
Reimbursement Form	Directly after baseline, 3 month follow-up, 6 month follow-up	Directly after baseline, 3 month follow-up, 6 month follow-up	N	Kept in Participant Folder locked in [name]'s office

12.3 General Instructions for Completing Forms

In order to consistently collect data information, interviewers will complete a training with [name] and or [name]. Research Manager, [name], will check forms once a month to assure that forms are filled out correctly.

12.4 Data Flow

Data will be entered into the online database (currently in Excel, considering moving to Access). With Excel, each person will need to alert the next team member when it is time for that person to act. For example, the Research Manager will need to e-mail the interviewer to set up an interview after the potential participant has agreed to conduct the baseline study. If that person is in the intervention group, the Research Manager will need to alert the OC-HE through an e-mail to establish a contact. This process will be monitored weekly through meetings with the PI, Research Manager, Interviewer, and OC-HE present.

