9.0 Blinding and Unblinding (Masking and Unmasking)

The student interviewer/data entry assistant will be blinded on who is chosen by random for the intervention group and will not know whose information belongs to whom.

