13.2 Quality Control Procedures

The PI and Co-PI will be responsible for quality assurance, performing internal quality management of study conduct, data collection, documentation and completion.

Quality control (QC) procedures will be implemented as follows:

Informed consent --- While there is no signed consent document, the Research Manager will train interviewers on explaining the informed consent letter. Most interviews are not recorded until after the participant has given informed consent, so the Research Manager will not be able to listen to recordings. The Research Manager will attend 10% of the interviews with the student interviewer to assure that the interviewer is reading through the letter with accuracy and completeness. Feedback will be provided to the study team to ensure proper consenting procedures are followed.

Source documents and the electronic data --- Data will be initially captured on source documents (see **Section Error! Reference source not found.**, **Data Handling and Record Keeping**) and will ultimately be entered into the study database. To ensure accuracy, site staff will compare a representative sample of source data against the database, targeting key data points in that review. Interviewers will enter data directly into Qualtrics. Each session will be recorded and 20% of the interviews (21 interviews) will be re-entered and compared to check the accuracy of data entry.

Intervention Fidelity — Consistent delivery of the study interventions will be monitored throughout the intervention phase of the study. Procedures for ensuring fidelity of intervention delivery are described in **Section Error! Reference source not found., Interventionist Training and Tracking**.

Protocol Deviations — The study team will review protocol deviations on an ongoing basis and will implement corrective actions when the quantity or nature of deviations are deemed to be at a level of concern.

Should independent monitoring become necessary, the PI will provide direct access to all trial related sites, source data/documents, and reports for the purpose of monitoring and auditing by the sponsor/funding agency, and inspection by local and regulatory authorities.

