15.0 Data and Safety Monitoring Activities

Given the nature of this study, single-site minimal risk trial, the [name] (PI) will be responsible for ensuring participants' safety on a daily basis. The Data and Safety Monitoring Board (DSMB) will act in an advisory capacity to monitor participant safety, evaluate the progress of the study, to review procedures for maintaining the confidentiality of data, the quality of data collection, management, and analysis.

The PI will meet with the research team weekly to conduct ongoing data and safety monitoring, and will meet bi-annually with the Data Safety Monitoring Board (DSMB) consisting of three external board members, Drs. [name], [name], and [name]. The PI will be informed of serious adverse events (SAEs) as soon as they occur and will notify the UI IRB and NIA within 24 hours of notification.

The DSMB will hold a minimum of two web-based conference calls per year (about two hours per call) to discuss protocols, progress of the intervention and research activities, and data and participant safety. The PI will prepare a Safety Report to be circulated prior to the scheduled call for DSMB members to review. The reports will contain information and analyses of study procedures, progress, and data and safety issues. The board members will review the study protocol and information presented in the report and will provide recommendations on recruitment, retention, quality control, and safety procedures while ensuring the confidentiality of the study participants and results. Through these activities, we will ensure that all

protocols are conducted in compliance with the AE and SAE guidelines and reports are sent to appropriate individuals including the University of Iowa IRB and the Program Officer at the NIH.

The content of the data and safety monitoring report will include: a brief summary of study organization, purpose and procedures, overall study status, participant enrollment and retention, reasons for non-participation, aggregated descriptive information of the participants, changes to study protocol, quality of collected data, status of data management, incidence of ADs/SAEs/unexpected problems and actions taken, and updated study timeline. The design of this study does not involve masking.

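### The protocol both blinds the student interviewer and says there is no masking, and the weekly meeting with the interventionist leaves that blinding unprotected; concealment of upcoming assignments from enrolling staff is also not assured

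*Protocol*

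**What the plan says.** On blinding, the Protocol makes two statements:

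- Section 9.0: "The student interviewer/data entry assistant will be blinded on who is chosen by random for the intervention group".
- Section 15.0, closing the description of the monitoring report: "The design of this study does not involve masking".

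The SAP does not mention blinding.

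On workflow, Protocol section 12.4 describes how staff alert one another when the next step is due. One step exists in one arm only. For a participant in the intervention group, "the Research Manager will need to alert the OC-HE through an e-mail to establish a contact". The section then says of the whole chain: "This process will be monitored weekly through meetings with the PI, Research Manager, Interviewer, and OC-HE present".

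On allocation, section 8.0 specifies 1:1 assignment from computer-generated random numbers after the baseline assessment. The Research Manager keeps the master list, assigns the codes and notifies staff, and the code is held in a computerized log apart from the study data. Section 6.0 names the Research Manager and the student interviewer as the two people who discuss the study with potential participants.

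**The concern.** Caregiver burden is named in the primary objective (section 1.0), and section 5.0 bases the power statement on it. It is self-reported. Under the scripts in Appendix V an interviewer conducts all three surveys in person or by phone, and section 13.2 says "Interviewers will enter data directly into Qualtrics". An interviewer who knows the arm can affect how questions are put, probed or recorded. Blinding that person is the protection section 9.0 offers, and a reader of the Protocol cannot tell whether it was part of the design or how it was kept.

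The list raises a separate risk. If someone who talks to candidates before enrolment can see the next assignment, that knowledge can influence who enters and when. This would be selection at entry, which blinding at follow-up does not repair.

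**Working it through.** No arithmetic applies. The check is to set the passages side by side.

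**1. Do the two masking statements conflict?** Section 9.0 blinds one named role. Section 15.0 denies masking for the design as a whole. The second may have been meant for participants and the interventionist, who cannot be masked here, but it is not limited to them. As worded both cannot hold, and no available passage reconciles them.

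**2. Is the interviewer of section 12.4 the person blinded in section 9.0?** Names are redacted, so this is an inference. Section 13.2 uses both terms for one person in one sentence: "The Research Manager will attend 10% of the interviews with the student interviewer to assure that the interviewer is reading through the letter". Section 6.0 pairs a single student interviewer with the Research Manager. The roles appear to be the same. Section 9.0 also says that the blinded person will not know whose data are whose. That does not fit someone who interviews participants directly (Appendix V) and collects reimbursement information (section 12.5) on a form bearing name and address (section 5.0).

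**3. Can allocation reach the interviewer at the meeting?** The monitored process includes a step that only intervention participants trigger. The Research Manager, who knows the assignments, and the interventionist, who knows whom she is treating, both attend. The interviewer has a legitimate reason to be there, since interview scheduling is part of the same chain. No available passage excludes the interviewer from the intervention-tracking items or requires them to be handled without identifying participants. The meeting is therefore a possible route to unblinding.

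**4. Which outcomes are exposed?** Those that an interviewer administers. Appendix V says this covers all three surveys, whereas section 12.1 says most questionnaires will be online, so the extent is unsettled. Use of medical services comes from the electronic record (section 6.1) and is largely outside the concern.

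**5. Who holds the list, and who meets candidates?** Sections 8.0 and 6.0 give both tasks to the Research Manager. On screening the documents disagree. The contact-form row of section 12.2 gives it to the Research Manager. Sections 5.0 and 5.1, and the eligibility row of section 12.2, give it to a research assistant. The overlap that stands without dispute is between keeping the list and discussing the study before assignment. Randomizing after baseline and storing the code separately do not, as described, hide future assignments from the person who keeps the list. Section 8.0 does not say whether the list shows them.

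**The case against.** The strongest reply is that this is loose wording and not a defect. Section 15.0 can be read as saying that participants and the interventionist are unmasked, leaving section 9.0 intact. The hand-off is an e-mail from the Research Manager to the interventionist, and nothing says that arms are discussed at the meeting. Section 8.0 refers to an automated log and a blinded code. The study protocol mentioned in section 2.0, the Data Management Plan (section 13.0) and the list of personnel responsibilities (Appendix T) are not in the text available, and any of them might supply the safeguard. Participants know their arm anyway, and the follow-up scripts open with a general question that could lead them to mention the program. A blinded interviewer removes only part of the possible bias.

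Much of this stands, and it sets the limits of the point. It does not remove the conflict as worded, or the absence from section 12.4 of any rule keeping allocation from the interviewer. Section 10.0 reserves by-group DSMB reports to the statistician, so some restriction on arm information was intended; that restriction does not cover the weekly meeting.

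Three stronger readings are tempting and not supported:

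- *That the interviewer was unblinded, or that concealment failed.* The documents show missing safeguards, not events. Discretion at entry is also limited: clinicians make the diagnosis and identify patients (section 5.1), and the screener is a short checklist (Appendix B).
- *That the list holder plainly screens.* The documents disagree, as shown above.
- *That the Research Manager's attendance at 10% of interviews is a second leak at follow-up.* Section 13.2 ties attendance to the reading of the consent letter. In Appendix V that reading appears only in the baseline script, before randomization, and section 6.0 merely offers a new copy later. Section 12.2 leaves some doubt ("Read through with Interviewer before baseline and revisited before 3 and 6 month follow up"). The same section's re-entry sample ("20% of the interviews (21 interviews) will be re-entered and compared") implies 21 / 0.20 = 105 interviews, close to one for each of the 106 planned participants, which suggests one wave. In any case, attending an interview does not reveal an arm.

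**Conclusion.** The concern holds in a limited form. The two masking statements conflict as worded, and the workflow leaves the blinding in section 9.0 unprotected for interviewer-administered outcomes such as caregiver burden. This rests on reading the interviewer of section 12.4 as the student interviewer of section 9.0, which sections 6.0 and 13.2 support, and on surveys being given by an interviewer, as Appendix V says.

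The secondary point is weaker. Concealment from enrolling staff is not assured, because the list holder also discusses the study with candidates and the visibility of upcoming assignments is not described. It is not shown to have failed.

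No size of bias can be derived, and none is claimed. Counting the interviews concerned would describe exposure, not bias.

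**What to change.** If the procedures can still be changed:

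1. Take the allocation and intervention-tracking items of the weekly meeting without the interviewer, and say so in section 12.4.
2. Have an existing team member who does not screen, consent or interview keep the list and release each assignment once baseline is complete, and say so in section 8.0. The statistician, who already prepares by-group reports under section 10.0, is one possibility; the documents do not say whether this person is available. The Research Manager can still make the hand-off to the interventionist after release.
3. Reconcile sections 9.0, 12.4 and 15.0 into one statement: the outcome interviewer is blinded; participants and the interventionist are not.

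The cost is a split agenda, one duty moved among existing staff, and a few sentences of text.

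Section 2.0 planned to finish data collection in March 2021, and the SAP is dated January 2022, so these changes may come too late. In that case, report who knew allocation and when, and how assignments were released. Do not claim assessor blinding or allocation concealment without evidence. A comparison of the arms at baseline would not supply that evidence, since balanced arms do not show that assignments were hidden. The cost is then one reporting paragraph.
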